To ensure maximum safety, the traceability of the product will be provided with lot number of Ketamine or informed administered Placebo on a pre established for each patient, form that you will find in the appendix to the project.

Any potential adverse event will be supported by physicians anesthesiologists responsible resuscitators of post operative monitoring of the hospital Raymond Poincaré, then transmitted instantaneously in pharmacovigilance and to the ANSM.

Clinical and paraclinical evaluation during the test.

Before administration of ketamine, we will evaluate clinical way:

The intensity of neuropathic pain evaluated at the moment on a numeric scale of 10 points at H0.

The score NPSI Neuropathic Pain Symptom Inventory comprising 12 questions, each question will be analysed: burning pain, pain to type of vise, compression pain, number of hours painful in the past 24 hours, such painful crises of electrical discharges, painful crises in type of knife, number of painful crises in the last 24 hours, presence of pain caused or increased pressure on the painful area, presence of pain caused or increased by the contact with a cold object on the painful area, presence of stinging, tingling presence.

HADS depression scale with 14 questions: Seven concerning anxiety and seven concerning depression.

The painful area evaluated on mapping by the subject before administration of ketamine then during follow-up.

Paraclinical:

A blood sample will be realized before the infusion of ketamine with dosage of: serotonin (5-HT), kynurenine (KYN), indoleamine 2, 3-dioxygenase 1 (IDO1) activity (ratio KYN/TRP), kynurenic acid (KA) and quinolinic acid (QA). as well as 3 proinflammatoires cytokines it-

1 β , IL-6, and TNF - α . then a new dosage to 4 hours from the end of the infusion in the hospital or outpatient service and will include the dosage of: serotonin (5-HT), kynurenine (KYN), indoleamine 2, 3-dioxygenase 1 (IDO1) activity (ratio KYN/TRP), kynurenic acid (KA) and quinolinic acid (QA), as well as 3 proinflammatoires cytokines it-1 β , IL-6, and TNF - α .

Duration of participation of the subjects:

The protocol will take place in the post operative monitoring room for infusion with 2-hour infusion, care of one hour after the end of the infusion in post operative room and then four hours in the hospital.

Either a minimum of passage to the hospital in 7 hours.

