As defined above, any adverse product will lead to the immediate cessation of the infusion however the patient will be analysed in the study for an intention to treat analysis. If it refuses the analysis or withdraws consent at any time of the study patients will be excluded from the study in accordance with best practices.

After the duration of 7 days of participation and follow-up, the patient will be released the study as planned in the Protocol (end of final follow-up).

Data collected on patients:

These data will include: full name, Date of birth, the patient's Age, height, weight, BMI, sex, usual treatments, Presence of allergy, medical conditions, age of evolution of chronic pain, spinal cord injury, the more important pain in the week prior to the inclusion. Score NPSI, HADS Score, painful Surface evaluated on mapping, Patient having already benefited from infusion of ketamine before, history of use of other non-drug therapies for treatment of chronic pain.

The data collected during the study will be for 7 days with the periods already mentioned: Score of NPSI on H0, J1, J4, J7, NPSI underscore; H0, J1, J4, J7, Score of depression HADS J0, J7 (for all elements in H1 and H4 previous evaluation by the clinician investigator, J1 J4 J7 by a self-report filled at home or by telephone call) Painful surface evaluated on H0, J1, J4, J7 (H1 and H4 by the clinician investigator, J1 J4 J7 by the patient at home on a sheet displaying the human body).

Regarding the lost to follow-up and missing data, the most pejorative result already gathered about each score will be taken as a reference to complete missing data, for analysis by intention to treat.

Two blood samples will be carried out on each patient. The first will arrive in SSPI before infusion of ketamine. The following sample will be 4 hours after the end of the infusion or 6 hours after the start of the infusion in outpatient service. Sampling and dosing methodology is explained below.

In addition 24 samples will be collected without ketamine infusion (12 patients with bedsores and 12 without), to assess the effect of inflammation on kynurenine pathway.

Methodology of dosage

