In the follow-up phone calls and self-report at home will be considered follow-up. Missing data management has already been clarified above.

Assessment of treatment effectiveness

The effectiveness of the treatment will be judged on a reduction of more than 30% of the intensity of neuropathic pain evaluated at the moment on a numeric scale of 10 points between H0 (before infusion) and H4 (after the end of the infusion). This criterion will be assessed by one of the investigators of the study.

Assessment of the safety of the treatment

Infusion being made in recovery room, the usual follow-up of a patient in recovery room will be arranged: decision-making of the constants every 15 minutes including the oxygen saturation, blood pressure, heart rate, awareness of Glasgow score, the respiratory rate. Supervision of one hour after the end of the infusion will be implemented.

The release of recovery room will be one hour after the end of the infusion and with the usual criteria of output with Aldrete score.

Any adverse event during infusion will be reported to a doctor Anaesthesiologist resuscitator and will be declared.

If an adverse event occurs a period of hospitalization is equal to 5 times the half-life (3 hours about ketamine), more than 15 hours will be organized until total elimination of the product.

Sample size and statistical analysis

After data from a study underway by our team (study LIKE), the standard deviation of instant pain score is of 1.4 on the same model. We considered that an improvement of 30% in the score of the intensity is relief significant clinic. Based on these figures and assuming a risk $\alpha = 0.05$ and a risk $\beta = 0.90$, and using a one-sided Student's T test for a comparison of the 2 to 2 groups the minimum calculated sample size is 12 patients analyzed per group (for a total of 48 patients).

After checking the normality of distributions, comparison of continuous variables (Score, NPSI, pain, depression and biology Score) between the two groups will be analyzed with the Student's T test, variables with a no normal distribution will be analyzed with the non-parametric Mann-Whitney U test. p < 0.05 was considered statistically significant p-values. R and SPSS software will be used for the production of statistics.

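### The effect of inflammation on the kynurenine pathway is assigned to 24 samples of undefined source (12 vs 12), and the plan does not say that the 48 pre-infusion samples (24 vs 24) will be used for it

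*Combined protocol and SAP*

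**What the plan says.** **Samples named for the inflammation question.** Under *Data collected on patients*, in a sentence introduced as an addition to the samples already described: "24 samples will be collected without ketamine infusion (12 patients with bedsores and 12 without), to assess the effect of inflammation on kynurenine pathway". No other sample set in the document is given this purpose. The sentence does not say whether the 24 come from the placebo groups or from people outside the trial, and it gives no entry criteria for them.

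**Samples every trial patient gives.** The paragraph just before it reads: "Two blood samples will be carried out on each patient. The first will arrive in SSPI before infusion of ketamine". Under *Clinical and paraclinical evaluation during the test*: "A blood sample will be realized before the infusion of ketamine with dosage of: serotonin (5-HT), kynurenine (KYN"), followed by the KYN/TRP ratio, kynurenic and quinolinic acid, IL-1β, IL-6 and TNF-α. *Secondary evaluation criteria* lists the same panel before and after administration. The diet and handling rules in *Methodology of dosage* apply to blood samples in general.

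**Group sizes.** *Population* defines four groups: with bedsore on ketamine or placebo, and without bedsore on ketamine or placebo. *Sample size and statistical analysis* gives "12 patients analyzed per group (for a total of 48 patients").

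**Analysis.** The same section compares continuous variables, biology included, between two groups by Student's t or Mann-Whitney. It does not say which two of the four groups are meant, and it names no bedsore vs no-bedsore contrast.

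**The concern.** That inflammation activates the kynurenine pathway is a premise of the trial's rationale. The bedsore vs no-bedsore comparison of the markers, before any study drug, is where the trial can check that premise in its own patients. The plan attaches the question to 24 samples and is silent on the 48 H0 samples that could answer it with at least twice the numbers per stratum.

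An analyst following the text literally would run 12 vs 12. That comparison has a wide confidence interval and misses moderate differences more often than not. An analyst who instead used the H0 samples, or pooled everything, would be making a choice that the plan does not record. The result would depend on a decision that can be taken after the data are seen.

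**Working it through.** **1. The plan's own figure.** The only sample-size calculation is for pain. Inputs: SD 1.4, one-sided α 0.05, power 0.90, and a 30% improvement. The baseline score for the 30% is not stated. Taking the entry minimum of 6 as an assumption gives 0.30 × 6 = 1.8 points.
- Normal approximation: n = 2 × (1.645 + 1.282)² × (1.4/1.8)² = 10.4, so 11 per group.
- Exact noncentral t: 12 per group (power 0.92), matching the stated 12.

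So 12 per group is a number for pain. No calculation supports 12 vs 12 for the kynurenine markers.

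**2. Counting pre-infusion samples.**
- With bedsore: 2 groups × 12 = 24.
- Without bedsore: 2 groups × 12 = 24.
- Total 48, against 24 (12 vs 12) named for the inflammation question.

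**3. Precision.** For equal groups of n and a common SD, the standard error of the difference is SD × √(2/n).
- n = 12: √(2/12) = 0.408 SD.
- n = 24: √(2/24) = 0.289 SD.
- Ratio 0.289/0.408 = 0.707, a reduction of 29%. This needs no assumed effect size.
- The 95% CI half-width (t quantile × standard error) falls from 0.85 to 0.58 SD.

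**4. Power.** Two-sample t-test, two-sided α 0.05, noncentrality d × √(n/2), degrees of freedom 2n − 2. For d = 0.8 the noncentrality is 0.8 × √6 = 1.96 at n = 12 and 0.8 × √12 = 2.77 at n = 24. The standardised differences d are assumptions, because the documents give no SD, effect size or power target for these markers.

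| | 12 vs 12 | 24 vs 24 | 36 vs 36 |
|---|---|---|---|
| Detectable d, 80% power | 1.20 | 0.83 | 0.67 |
| Detectable d, 90% power | 1.39 | 0.96 | 0.78 |
| Power, d = 0.5 | 22% | 40% | 55% |
| Power, d = 0.8 | 47% | 77% | 92% |
| Power, d = 1.0 | 65% | 92% | 99% |
| Power, d = 1.2 | 80% | 98% | >99% |

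The last column applies only if the 24 are new people who can properly be combined with the trial patients (24 + 12 = 36 per stratum). With a one-sided test, as in the pain calculation, power at d = 0.8 is 60% for 12 vs 12 and 86% for 24 vs 24, so the conclusion is the same.

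**5. What the text allows.**
- (a) 24 new people analysed alone: the 48 H0 samples go unused for this question.
- (b) 24 new people added to the H0 samples: 36 vs 36, but this is not written down.
- (c) The placebo patients, whose groups are also 12 and 12: the ketamine patients' H0 samples go unused.

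Samples are lost under (a) and (c). Under (b) nothing is lost, but the analysis set is unwritten.

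**The case against.** A reader might infer that the inflammation question is to be judged on these 24 samples alone and that the H0 samples are deliberately set aside. The documents do not say that. The sentence opens by presenting the 24 as additional to the two samples per patient, no section excludes the H0 samples, and the pre-infusion assays are listed among the secondary criteria. Reading (b) is open, and under it no data are discarded. This objection stands against any claim that the plan chose the smaller analysis. It does not supply the missing statement: the 24 are still the only set tied to the question, and no bedsore contrast is named.

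Three further limits stand.
- **Pooling is not automatically sound.** Unlike the four trial groups, the 24 are described only by bedsore status, with no mention of neuropathic pain or of entry criteria. Combining people of different eligibility could confound the comparison.
- **The stakes are limited.** Main objective 2 concerns ketamine's own action through the pathway, which is measured before and after infusion. The baseline bedsore contrast supports that objective but does not decide it.
- **No saving in assays can be promised.** The trial's H0 and H4 samples are needed in any case.

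**Conclusion.** The point holds in this form: the plan ties the inflammation question to 24 samples of undefined source and does not say that the 48 H0 samples will be used. Taken literally, that is 12 vs 12. Naming all H0 samples as the analysis set gives 24 vs 24, with the gains shown above: standard error 29% lower, and detectable difference at 80% power 0.83 instead of 1.20 SD.

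This rests on full enrolment with complete H0 sampling, equal variances, the t-test, and assumed standardised differences where power is quoted. The gain is realised only if the H0 samples would otherwise have been left out, which the text permits but does not state.

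Two cautions apply at any sample size. Bedsore status is not randomised, so the comparison is observational. The H0 samples are free of study ketamine, but not necessarily of all ketamine: earlier infusions are recorded and no washout is stated.

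The change should be made because it improves precision at no cost and closes an analysis choice that is now open. It does not affect the primary endpoint.

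**What to change.** 1. In *Sample size and statistical analysis*, define the inflammation analysis as bedsore vs no bedsore on the H0 samples of all 48 randomised patients, ketamine and placebo arms together, and describe it as a non-randomised comparison.
2. In *Data collected on patients*, state whether the 24 samples come from placebo patients or from new people.
   - If placebo patients: say that their H0 samples are already within the 24 vs 24.
   - If new people: give their eligibility and sampling rules and the reason they are needed. Add them to the main comparison only if those rules match the trial's; otherwise analyse them separately as a sensitivity analysis.
3. Report previous ketamine use by bedsore stratum alongside the result, since it is already recorded.

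Cost: a few sentences. The H0 samples and assays are already planned, so no new data are needed.

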The kynurenine pathway is the way of tryptophan metabolism (figure 1). This path is involved both in depression and pain, two diseases often associated (1). The indoleamine 2, 3-dioxygenase (IDO) is an enzyme modulating the kynurenine metabolism. It has been shown that inflammatory cytokines may activate IDO, which would induce a decrease tryptophan by direction preferred to the path of the kynurenines, which can lead a deficit in serotonin and in consequence depression (2). One of the products of degradation of the kynurenine is quinolinic acid, a NMDA agonist receptors. NMDA receptors are involved in Central sensitization of the pain with as consequence an amplification of the painful message manifesting by an hyperalgesia.

2) Kynurenine pathway activation by inflammation.

A large number of experimental studies showed the important role of pro-inflammatory factors in the pathogenesis of chronic pain and depression (3-6). The role of the pro-

inflammatory cytokines in the activation of the indoleamine 2, 3-dioxygenase (IDO) was widely reported and is a key action in the pathophysiology of the comorbidity of pain and depression (7-9).

Several experimental and clinical work related the IDO enzyme is activated by systemic inflammation (10). This activation is found in several chronic inflammatory diseases (cancers, rhumathologic, inflammatory cardiovascular diseases). More recently its activation was highlighted in patients with the irritable bowel syndrome (11,12). This path seems to activate quickly in the early hours after tissue trauma in models of various surgery (coronary bypass surgery, thoracic surgery, hysterectomy) (13,14).

3) Interaction of ketamine on kynurenines.

There are many mechanisms of action for ketamine. But more recently efficacy of ketamine in inflammatory so-called depressions and experimental studies addressing the inflammatory aspects common pain and inflammation have attracted our attention to the kynurenine pathway (15) (figure 1). Ketamine has shown a role towards the kynurenines in models of experimental pain (9,16,17). The ketamine has an antidepressant effect in fast action potentially by the inhibition of proinflammatory cytokines (18,19)(20). The rate of Interleukin 6 plasma would be predictive for efficiency of ketamine in a depressed patient population (21). Although there is a beam of clinical and paraclinical arguments about the role of IDO in the

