A temporary stoppage of the study will be considered when new fact (as defined above) in order to give himself time to reassess the balance of benefits and risks of research jointly with ANSM .

Ratings criteria

Main evaluation criterion

Decrease (more than 30%) the intensity of neuropathic pain evaluated at the moment on a numeric scale of 10 points between H0 and H4.

Secondary evaluation criteria

Score of NPSI on H0, J1, J4, J7 Under the NPSI score; H0, J1, J4, J7 Score of depression HADS or Hamilton J0, J7 Pain timeline between J0 and J7. Painful surface evaluated on mapping H0, J1, J4, J7 Decrease in scores between baseline and H4. Side effects of the drugs evaluated H0 and H4 of the end of the infusion then in J1. Auto assessment of relief of pain and mood improvement at 7 days after infusion. Blood assays pre administration of Ketamine then H4 after end of Directors of: serotonin (5-HT), kynurenine (KYN), indoleamine 2, 3-dioxygenase 1 (IDO1) activity (ratio KYN/TRP), kynurenic acid (KA) and quinolinic acid (QA), as well as 3 proinflammatoires cytokines it- 1β , IL-6, and TNF - α

Patient selection, exclusion and data collected.

The criteria for inclusion:

- SCI with central neuropathic pain with or without bed sores.
- Adults speaking and understanding the French
- With chronic neuropathic pain, according to the IASP definition
- Painful intensity > or = 6 / 10 during the week prior to the inclusion
- Spinal cord injury a few either the origin (traumatic, degenerative, tumor, post operative), responsible for paraplegia in a chronic state.
- Able to give their informed consent after a clear, fair and appropriate information
- Having given their agreement by a written consent signature.

No inclusion criteria:

- Patients with a hypersensitivity to ketamine or one of its excipients.
- Another Interventional trial participation, or participation in another trial interrupted for less than 3 months.

- Patient unable to give their consent
- Pregnancy or lactation underway
- Refusal of consent signature
- Cardiovascular diseases particularly associated with rhythm disorders and severe heart failure, coronary, discovered by examination, ECG or biological assessment or known.
- HTA unstabilized > 180/100 mmHg
- Severe hepato cellular and / or renal failure.
- For the group without sores, lack of ongoing inflammatory pathology noted by the interrogation (fever, sepsis, urinary tract infection)

Exclusion criteria:

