Blood samples will be collected after 48 h of a diet serotonin (avoid bananas in particular) and tryptophan (chocolate to be avoided) in Vacutainer 7 mL containing EDTA tubes. After gentle inversions of the tubes (agitation brutal would cause damaging platelet activation with the determination of serotonin, almost exclusively contained in platelets) total 500 µL of blood are immediately frozen (-20 ° C or - 80) (° C). The rest of each sample is centrifuged at 4 ° C and 2500 g for 15 minutes and the resulting plasma is aliquote under 500 µL and frozen at-80 ° C until analysis. Blood serotonin and tryptophan plasma will be measured by HPLC(31). Kynurenic acid and kynurenine will be also measured by HPLC according to Fujigaki, Swartz and al and al respectively(32.33). For his part, quinolinique acid will be measured by LC - MS(34). The kynurenine/tryptophan ratio will be conventionally used as index of activity IDO1.

Cytokines illbeta, IL6 and TNFalpha will be measured by electrochimiluminescence on a multiplex platform (35).

Drugs allowed or stopped during and before the test

Our population being affected by chronic pain, many treatments to target pain are generally used. The usual treatment of patients will be continued before, during and at the end of the study.

Painkillers of tier 1, 2 or 3. Anti epileptic on pain neuropathic, antidepressants (SSRIS, MAOIS, tricyclics...). None of these drugs will prohibit participation in the study however we will proceed with a compendium of the various treatments by patients.

Ketamine can potentiate the neuromuscular blocking atracurium and the tubocurarine including respiratory depression with apnea. The concomitant administration of ketamine with halogenated anesthetic agents may extend the elimination half-life of ketamine and delay the recovery phase. Our patients are not surgical patients, none will have received this type of product before the infusion.

Co-administration of the phylline may lower the convulsive threshold. No administration of The phylline is scheduled.

Only bananas and chocolate will be an eviction during the 48 hours preceding blood sampling in order not to distort the dosages of serotonin and tryptophan.

Procedures to assess compliance of subjects to treatment

The infusion being in post operative monitoring room for a period of two hours. Compliance assessment can be done without bias.

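### Whole-blood serotonin is compared with no platelet count recorded, so a bedsore-group difference in serotonin cannot be told apart from a difference in platelet count

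*Combined protocol and SAP*

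**What the plan says.** In *Methodology of dosage*, blood is drawn into 7 mL EDTA tubes. An uncentrifuged 500 µL aliquot "of blood are immediately frozen", and the rest is spun down to plasma. The assay sentence reads "Blood serotonin and tryptophan plasma will be measured by HPLC(31", so serotonin is a whole-blood measure and tryptophan a plasma measure. The same paragraph asks for gentle inversion of the tubes because rough handling would disturb "the determination of serotonin, almost exclusively contained in platelets".

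No platelet count appears among the assays in *Clinical and paraclinical evaluation during the test* or in *Secondary evaluation criteria*. The list in *Data collected on patients* begins "These data will include: full name, Date of birth, the patient's Age, height, weight, BMI, sex, usual treatments, Presence of allergy, medical conditions" and continues with pain history and scores, without a blood count. The nearest item is in the non-inclusion criteria, where cardiovascular disease may be "discovered by examination, ECG or biological assessment or known". The content of that assessment is not itemised, and no analysis uses it.

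On the use of the measurements, *Data collected on patients* sets out a comparison by bedsore status: "In addition 24 samples will be collected without ketamine infusion (12 patients with bedsores and 12 without), to assess the effect of inflammation on kynurenine". The *Rational* section says that activation of IDO by inflammation diverts tryptophan, "which can lead a deficit in serotonin and in consequence depression". *Sample size and statistical analysis* compares biology variables between two groups by Student's t or Mann-Whitney test and names no covariate.

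**The concern.** If nearly all the serotonin in blood sits in platelets, the level in a fixed volume of whole blood depends on two things: how many platelets there are and how much serotonin each holds. The plan uses the platelet location to justify tube handling but carries it into neither the data collected nor the analysis.

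Two consequences follow. First, variation in platelet count between patients adds noise to every comparison of serotonin levels, in groups of about 12. Second, bedsore status is not randomised, so nothing balances platelet counts between patients with and without bedsores. A difference in serotonin there, or the absence of one, has two possible explanations that the recorded data cannot separate. The frozen aliquots are not described as usable for a later count, so the information has to be captured at sampling.

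**Working it through.** **1. The plan's own figure.** The plan gives no sample size, variance or expected difference for serotonin. Its 12 per group is for pain. With SD 1.4, a 30% improvement on an assumed baseline of 6 (the inclusion floor) is 0.30 × 6 = 1.8 points. At one-sided α = 0.05 and power 0.90, the normal formula gives n = 2 × (1.645 + 1.282)² × 1.4² / 1.8² ≈ 10.4, so 11 per group, and the exact t calculation gives 12. The figure is reproduced and nothing below changes it.

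**2. Model.** Write B = P × c, with B the serotonin per volume of blood, P the platelet count and c the serotonin per platelet. This follows from the plan's statement on location. The per-volume reading is inferred from the fixed 500 µL aliquot, because no unit is stated.

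**3. Bedsore comparison.** Let d be the true relative deficit per platelet in bedsore patients and x the relative excess in their mean count. The apparent ratio is (1 − d)(1 + x). The documents give neither d nor x, so all values are assumptions. For d = 0.20:

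| x | Apparent difference in B |
|---|---|
| −10% | 0.80 × 0.90 − 1 = −28% |
| 0 | −20% |
| +10% | −12% |
| +20% | −4% |
| +30% | +4% |
| +40% | +12% |

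The deficit that an excess x exactly hides is 1 − 1/(1 + x): 9.1%, 16.7% and 28.6% for x = 10%, 20% and 40%. A lower count exaggerates the deficit instead. With d = 0, the apparent difference is simply x.

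**4. Noise.** If P and c are independent, the relative variance of B divided by that of c is approximately (CV_P² + CV_c²)/CV_c². For assumed CVs of 20% (count) and 40% (content) this is (0.04 + 0.16)/0.16 = 1.25. For 30% and 30% it is (0.09 + 0.09)/0.09 = 2.0.

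**5. Power, as an illustration.** Assume d = 30%, CV_c = 30%, CV_P = 25%, 12 against 12, and a two-sided 0.05 t test on the log scale. The log SDs are √ln(1.09) = 0.294 per platelet and √(ln 1.09 + ln 1.0625) = 0.383 per volume. The log difference is −ln 0.70 = 0.357 per platelet and 0.357 − ln(1 + x) per volume.

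- Per platelet: power 0.81.
- Per volume: 0.59 at x = 0, 0.36 at x = 10%, 0.19 at x = 20%, 0.08 at x = 30%.
- With no true deficit and x = 20%, a significant higher level in the bedsore group appears about 20% of the time, against 2.5% in that direction under no difference.

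**6. The opposite model.** Suppose instead that a fixed amount of serotonin is shared among however many platelets there are. Then B does not change with P, and c falls by 1 − 1/(1 + x): the same 9%, 17% and 29%. Dividing by the count would then create a deficit that is not there, in the direction the *Rational* predicts. The documents do not say which model holds.

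**7. Ketamine against placebo.** Randomisation balances P in expectation. Within a patient, ln B(H4) − ln B(H0) = [ln P(H4) − ln P(H0)] + [ln c(H4) − ln c(H0)]. If the count is stable over those hours, the first bracket is zero and the count drops out of the ratio. Both samples are already planned.

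**The case against.** A reader might infer that inflammation raises platelet counts in bedsore patients, so that the design hides a real serotonin deficit. The documents do not support that: nothing in them says that counts differ by bedsore status, in either direction. With equal mean counts only noise remains.

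A reader might also infer that serotonin per platelet is the correct measure and should replace the per-volume value. Step 6 shows why this fails. It assumes that content per platelet is independent of count, and otherwise it can create a false deficit. The variance ratio in step 4 rests on the same assumption. This objection stands, and it is why both measures should be reported.

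Other points also stand. No serotonin test of bedsore against no bedsore is explicitly specified. The statistical section refers to two groups without defining them and does not say whether levels or changes are compared. The 24 samples are collected "to assess the effect of inflammation on kynurenine pathway", and the plan's named IDO1 index is KYN/TRP. The serotonin deficit is background reasoning, not one of the two hypotheses under *Trial purpose and goal*. The assay line in the summary is not fully legible in the available text, so the matrix is taken from the detailed method. A routine blood count may exist within the eligibility work-up.

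None of this removes the core. Serotonin is a listed assay, it is taken on whole blood, and any comparison of its level between bedsore groups would be uninterpretable on this point without a count.

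**Conclusion.** The point holds as a minor one. Platelet count enters any between-patient comparison of serotonin levels, and the plan records nothing to account for it. In the non-randomised bedsore comparison, a serotonin difference and a platelet-count difference cannot be separated. The direction and size of any bias are unknown. The figures above show only how large the effect would be under assumed count differences of 10% to 40% and assumed CVs of 20% to 40%. The randomised ketamine-placebo comparison of serotonin is noisier but not biased. The pain endpoint, the sample size and KYN/TRP are unaffected.

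**What to change.** 1. For the ketamine effect, analyse serotonin on the log scale as H4 adjusted for H0, or as the H4/H0 ratio. The ratio cancels a stable platelet count, and the adjusted analysis removes the part that H0 predicts. This needs only wording in the statistical section.
2. Record a platelet count from each EDTA tube before freezing, or from a same-day blood count. Report serotonin per 10^9 platelets alongside the per-volume value, not in place of it, and state the matrix and unit once.
3. Read a bedsore-group serotonin difference as evidence on the pathway only if both measures agree. If no count exists, state that limit with the result.

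The cost is one automated count per tube on blood already drawn: 48 × 2 = 96, plus up to 24 if the additional samples come from other patients, so at most 120. No further venepuncture is needed.
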